## General Information

Walking impairment is a significant consequence of multiple sclerosis (MS) resulting in substantial limitations of daily activities and compromised quality of life. Energy expenditure of walking is elevated and may contribute to fatigue, which could further lead to a sedentary life style and secondary health deterioration. Thus, developing effective and efficient strategies to promote walking in this population is essential. Recently, wearable lower extremity exoskeleton has been developed to restore ambulation in paralyzed or weak individuals with spinal cord injuries. These exoskeleton robotic devices utilize the user's movements, such as body sway, to initiate externally powered gait and may reduce physical demands required for walking and provide great opportunity for persons with various conditions such as MS to walk independently. Therefore, the purpose of this pilot study is to investigate whether using exoskeleton could promote recovery of walking in persons with MS. Overall, we expect these findings to support that exoskeleton will demonstrate greater efficacy to facilitate walking and can be applied extensively to improve quality of life in MS.

## Background Information

The impaired ability to walk independently is a significant consequence of multiple sclerosis (MS) resulting in substantial limitation in mobility and performance of daily activities, thus restricting full participation and home and community re-integration [1, 2]. Moreover, the energy expenditure of walking is increased [3]. This additional metabolic demand contributes to fatigue, which promotes a sedentary life style that predisposes to secondary health deterioration and compromised quality of life. Gait training/restoration in MS is necessary but often limited due to the progress and severity of the disease and limitations of traditional strengthening exercises. Thus, developing novel strategies to promote independent walking in this population is essential for health promotion. Recently, *wearable* lower extremity robotic exoskeletons (exoskeleton) have been developed to restore ambulation in paralyzed or weak individuals with spinal cord injuries. Different from bodyweight supported robotic-assistance locomotion device integrated into a treadmill (such as Lokomat)[4], exoskeletons are designed to utilize the user's residual active movements, such as body forward and lateral sway, to initiate

externally powered stepping for over ground walking and climbing stairs. Most importantly, the assistance provided by wearable robotic exoskeletons may reduce energy expenditure during walking and allow persons with MS to recover some degree of independent walking that is more efficient. Needless to say, this can have a profound impact on quality of life. Therefore, the purpose of this pilot study is to investigate whether using exoskeleton could promote recovery of walking in persons with MS. We hypothesize that participants will be able to walk with exoskeleton and with minimal to moderate trainer assistance after training (Aim1). We also plan to determine and compare physical and cognitive demands during over ground walking with and without exoskeleton (Aim2). We hypothesize that physical and cognitive demands will reduce (i.e. decrease oxygen cost and shorter reaction time) during over ground walking with exoskeleton and especially after training. The reduced physical and cognitive demands will promote energy conservation and prevent/delay fatigue in over ground walking in this population. *The innovation of this study is this wearable exoskeleton provides a unique opportunity not only to assist a sustained upright posture but also facilitate walking with better energy efficiency in individuals with MS. Overall, we expect these findings to support that exoskeleton will demonstrate greater efficacy to facilitate walking and can be applied extensively to improve quality of life in MS.*

## Objectives

The purpose of this pilot study is to investigate whether using exoskeleton could promote recovery of walking in persons with MS. We hypothesize that participants will be able to walk with exoskeleton and with minimal to moderate trainer assistance after training (Aim1). We also plan to determine and compare physical and cognitive demands during over ground walking with and without exoskeleton (Aim2). We hypothesize that physical and cognitive demands will reduce (i.e. decrease oxygen cost and shorter reaction time) during over ground walking with exoskeleton and especially after training. The reduced physical and cognitive demands will promote energy conservation and prevent/delay fatigue in overground walking in this population. The wearable exoskeleton will be used in this study is Ekso®, by Ekso Bionics, formerly known as eLEGS®.

## Study Population

We will enroll 15 human subjects who have a diagnosis of MS confirmed by a neurologist. Potential subjects will be referred and recruited from affiliated MS neurology clinics, support group and other community neurologists. We will enroll persons with MS regardless of phenotype without evidence of clinical deterioration for at least 4 months prior to study entry.

Subjects will be enrolled if they meet the following inclusion criteria:

- Age 18 years or older
- Male or non-pregnant female
- Ambulatory with assistive devices (Ambulation status will be determined by the EDSS score)
- With an Expanded Disability Status Scale (EDSS) score [5] between 6 and 7.5 inclusive
- Height and weight are between 160 and 188 cm (5'2" to 6'2"), and less than 100 kg (220 lb), respectively (per exoskeleton manufacturer)
- Able to follow simple 3 step commands
- Able to understand the study procedure and consent form

Subjects will be excluded if they have any of the following exclusion criteria:

- History of severe neurologic injuries other than MS (SCI, CP, ALS, TBI, CVA, etc.)
- Severe comorbidities: active infections, heart, lung, or circulatory conditions, pressure ulcers
- Documented severe osteoporosis affecting the hip and spine
- Severe spasticity in the lower extremities (Modified Ashworth  $\geq 3$ ) or uncontrolled clonus
- Unhealed limb or pelvic fractures
- Skin issues that would prevent wearing the device

- Range of motion restrictions that would prevent subject from achieving a normal, reciprocal gait pattern, or would restrict a subject from completing normal sit to stand or stand to sit transitions.
- Upper extremity strength deficits that limit ability to balance with a front rolling walker or crutches.
- Heterotopic ossification that resists functional range of motion in lower extremities
- Contractures (>15 degrees at the hips or >20 degrees at the knees)
- Psychiatric or cognitive comorbidities resulting in motor planning or impulsivity concerns
- Colostomy
- Non-English speaking

### Study Design and Procedures

This study is designed to investigate whether using exoskeleton could promote recovery of walking in persons with MS. A total of 15 individuals with MS will be recruited for the study. Screening, assessment and treatment sessions will be held at TIRR, Memorial Hermann. Approximately 18 visits over a 1-month period will be required.

Detailed schedule of assessments is shown in Table.

Assessment	Pre Screening/ Screening	Baseline	Exoskeleton Training 5 session/week, 3 weeks, total 15 sessions	Post-treatment (Within a week)
	Visit 1	Visit 2	Visit 3-17	Visit 18
ICF	X			
I/E Criteria	X			
Demographics	X			
Medical History	X			
Mini Mental State Exam		X		X
Muscle strength		X		X
Range of motion		X		X
Barthel Index		X		X
Modified Ashworth Scale		X		X
Quality of life		X		X
Berg Balance Scale		X		X
Timed Up & Go Test		X		X
6-min walk test		X		X
Physical Demand Measure		X		X
Cognitive Demand Measure		X		X
Timed 25 Feet Walk Test		X		X
Physical Demand Measure		X		X
Cognitive Demand Measure		X		X
Exoskeleton training			X	

Borg Rating of Perceived Exertion Scale		X	
Pain scale		X	
Exoskeleton User Feedback			X

#### Recruitment:

Potential subjects will be referred and recruited from TIRR Memorial Hermann hospital and UT Multiple Sclerosis clinic ([name], co-investigator) during regularly scheduled appointments. Recruitment will also take place through flyers (see attached) posted at the TIRR Memorial Hermann facilities and the Greater Houston Metropolitan area. We will also post traditional and electrical advertisement on newspapers, the PI website, electronic bulletin boards, research center social media and list-serves. We will also perform targeted recruitment (for participants with MS) at TIRR Memorial Hermann hospital and UT Multiple Sclerosis clinic ([name], co-investigator).

Patients will be screened to determine potential eligibility and interest in participation.

#### Pre-screening:

Potential subjects will be screened over the telephone or in person using a survey form which includes a) demographic data; b) basic physical status; c) basic neurological history. The initial telephone or in person screening process will improve the efficiency of the study since it reduces the likelihood of unsuitable participants (i.e., participants meeting exclusion criteria) having to undergo a full screening before being excluded.

If the subject passes the pre-screening, the details of the study specific procedures will be reviewed with the subject. Subjects will be given an opportunity to review the information and ask questions. Once they have decided they are interested in participating in the study, they will sign the informed consent. Once informed consent is obtained, a letter to request approval to participate in the study will then be sent to the subject's physician (either neurologist or primary care physician). The subject's physician will verify the following medical status of the subject: subject's Expanded Disability Status Scale (EDSS) score, absence of clinical deterioration during the previous 4 months, non-pregnancy status of all females. After the research team receives the approval letter, the subject will be enrolled and baseline session will be scheduled. Each enrolled subject will be assigned an identification number.

#### Screening

Once physician clearance has been obtained, a screening visit will be scheduled. The screening visit will include an assessment of subject's flexibility in their arms and legs (range of motion), tension or resistance movement (spasticity) in arms and legs, strength in arms and legs, and physical measurements of hips and legs to ensure subject is able to safely fit into the robotic device. This visit will last about 30-45 minutes.

#### Baseline Functional Assessment:

After being medically cleared, screening visit completed and subject meets all inclusion criteria, the subject will be contacted to schedule an appointment for functional evaluations to quantify their motor impairment levels prior to training.

#### Outcome Measures

Subjects will perform the following measures before exoskeleton training and after training:

1. Barthel Index: This test measures the ability of a person with a neuromuscular or musculoskeletal disorder to care for him/herself. It is a 10-item questionnaire wherein each item is rated based on the

level of assistance required to complete the activity/item (with higher scores representing more functional independence).

2. Mini Mental State Examination: Folstein Mini Mental State Examination (MMSE) provides information about orientation, attention, learning, calculation, delayed recall, and construction.
3. Muscular Strength test: we will measure lower extremity muscle strength using force gauge such as handheld dynamometer. Subjects will lie down or sit on an examination table during testing based on the tasks. Subject will be asked to produce force to against the force gage at their maximal efforts for few times. Verbal encouragement will be provided for motivation. One minute or more resting time will be provided between trials.
4. Range of Motion: we will measure range of joint motion of bilateral hip, knee and ankle joints. Subject will lie down on an examination table. We will move the joint in the desired directions (flexion-extension, abduction-adduction, internal-external rotation) and we will measure the angle between start and stop position.
5. Modified Ashworth scale for spasticity: This test measures spasticity in patients with lesions of the Central Nervous System by testing resistance to passive movement about a joint with varying degrees of velocity. Scores range from 0-4, with 6 choices (i.e., 0, 1, 1+, 2, 3, 4), with 0 indicating normal muscle tone, and 4 indicating very high spasticity. This test has good reliability for determining spasticity levels in lower limbs after MS. During this test, subject will sit or lie down on a examination table. The examiner will move the tested joint several times.
6. Quality of Life Questionnaire: subject will fill out Multiple Sclerosis Quality of Life-54 (MSQOL-54). MSQOL-54 is a self-report questionnaire and a multi-dimensional health-related quality of life measure that includes the Health Status Questionnaire (SF-36) and 18 items for MS-specific issues such as fatigue and cognitive function.
7. Berg Balance Scale: A 14-item objective measure designed to assess static balance and fall risk in adult populations, with maximum summed score of 56 (higher scores represent better functional outcome). This task will be formed without using exoskeleton at pre-assessment and post-assessment.
8. Timed Up and Go Test: this task involves subject to stand from the standard chair, walk straight for 3 meters, turn around, walk back to the chair and sit down with shoes and assistive devices if any. A standard chair with arm rests will be place at the start of the testing course. A mark will be placed on the floor at the 3 meter distance. Subject will be asked to perform the task as fast as possible without losing their balance. One research member will stand next to the subject to monitor the subject performance to prevent falls. The time to complete the task will be measured and recorded. Subjects will also have recording of electromyography in the lower limbs i.e., sensors will be placed on the skin of the legs and thighs (4 on each leg) to non-invasively record muscle activity during walking. Additional sensors i.e., goniometers will be placed on the skin to non-invasively record joint angles of the hip, knee and ankle on each leg. These will be attached to the skin using hypoallergenic tape. This task will be formed without using exoskeleton at pre-assessment and with and without exoskeleton at post-assessment.

9. 6-minute walk test: Subjects will be asked to walk back and forth in a hallway with or without assistive device (consistent among assessment visits) for 6 minutes. The objective is to cover as much space as possible in 6 minutes. Subjects can slow down or stop to rest if they feel like, but should start walking when they feel they are able. Electromyography sensors will also be placed on the skin of the leg and trunk muscles to measure muscle activity. A research team member will walk behind the subject to prevent loss of balance during the test. This task will be formed without using exoskeleton at pre-assessment and with and without exoskeleton at post-assessment. In this tasks, we will measure physical demands and cognitive demand in separate trials or sessions:
  - A. Physical demands measures: Physical demands during walking with and without EKSO will be determined by oxygen cost. Oxygen cost will be calculated from oxygen consumption as the product of gait speed and body weight [10]. Oxygen consumption will be collected on a breath-by-breath basis measured by a portable metabolic system (K4 b2 Cosmed). Prior to the testing, the system will be calibrated using room air and reference gas mixture [11]. During the testing, the subject will wear a face mask and a heart rate monitor at all times and will be asked to breathe normally. The portable device will be carried by the subject at where it will not interfere with the walking (i.e. upper back or waist).
  - B. Cognitive demands measure: Cognitive demands during walking with and without exoskeleton will be determined by reaction time using a dual-task paradigm [12]. Dual-task paradigm is commonly used to quantify the cognitive (i.e. attentional) resources allocated during a motor task such as walking and usually entails reciting the alphabet or counting backwards [13]. However, this specific measurement is limited by structural issues involving respiration, vocal responses or motor action of the upper limb (push a button) for which there are shared execution pathways with locomotion [14, 15] could interfere with the primary motor task, despite not being caused by competing demands for limited attentional resources. Thus, we chose a simple reaction task (RT), in which the response will be biting on a pressure sensor to make the response pathways as independent as possible from the motor pathways of locomotion [12]. Subjects will with and without EKSO (use same assistive device) at their preferred speed. The secondary RT task consists of biting a pressure transducer placed in the mouth in response to an unpredictable sensory (will not cause pain) electrical stimulation applied by an electrode on the back of the neck [12] without changing walking speed and pattern. The stimulation intensity will be adjusted for each individual before data collection. Shorter RT indicates that reduced amount of attentional resources are required.
10. Timed 25 Feet Walk Test (T25-FW): this task will ask the subject to walk for 25 feet at comfortable pace. Subjects will wear their exercise or walking shoes and are allowed to use assistive device such as cane or walker if necessary. The start and finish line of the 25 feet test course will be marked with tape on the floor. Additional 5 feet at the end of start and finish will be used for subject to turn around. A chair will be provided next to the start area so the subject may rest. During the test, the subject will walk at his/her comfortable pace without losing balance followed by walking at maximal pace. Resting periods will be provided between trials. One trial for each pace will be performed. Trial will be repeated if subject cannot finish the task due to fatigue or loss of balance. A research team member will walk next to the subject for safety. The time to complete the tasks will be recorded. We will place markers on the skin of the legs and trunk and the marker data will be recorded by motion capture system. Electromyography sensors will also be placed on the skin of the leg and trunk muscles to measure muscle activity. This task will be formed without using exoskeleton at pre-assessment and with and without exoskeleton at post-assessment. A research team member will walk behind the subject to prevent loss of balance during the test. This task will be formed without using exoskeleton at pre-assessment and with and without exoskeleton at post-assessment. In this tasks, we will measure physical demands and cognitive demand in separate trials:
  - A. Physical demands measures: Physical demands during walking with and without EKSO will be determined by oxygen cost. Oxygen cost will be calculated from oxygen consumption as the product of gait speed and body weight [10]. Oxygen consumption will be collected on a breath-by-breath basis

measured by a portable metabolic system (K4 b2 Cosmed). Prior to the testing, the system will be calibrated using room air and reference gas mixture [11]. During the testing, the subject will wear a face mask and a heart rate monitor at all times and will be asked to breathe normally. The portable device will be carried by the subject at where it will not interfere with the walking (i.e. upper back or waist).

B. Cognitive demands measure: Cognitive demands during walking with and without exoskeleton will be determined by reaction time using a dual-task paradigm [12]. Dual-task paradigm is commonly used to quantify the cognitive (i.e. attentional) resources allocated during a motor task such as walking and usually entails reciting the alphabet or counting backwards [13]. However, this specific measurement is limited by structural issues involving respiration, vocal responses or motor action of the upper limb (push a button) for which there are shared execution pathways with locomotion [14, 15] could interfere with the primary motor task, despite not being caused by competing demands for limited attentional resources. Thus, we chose a simple reaction task (RT), in which the response will be biting on a pressure sensor to make the response pathways as independent as possible from the motor pathways of locomotion [12]. Subjects will with and without EKSO (use same assistive device) at their preferred speed. The secondary RT task consists of biting a pressure transducer placed in the mouth in response to an unpredictable sensory (will not cause pain) electrical stimulation applied by an electrode on the back of the neck [12] without changing walking speed and pattern. The stimulation intensity will be adjusted for each individual before data collection. Shorter RT indicates that reduced amount of attentional resources are required.

11. Exoskeleton satisfaction questionnaire: After completion of exoskeleton training sessions subjects will complete a survey of 9 questions regarding their experience with the exoskeleton and any feedback they would like to provide.

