#### Assessment of participant status after each training session:

Additionally, for every session, participant's physical comfort will be monitored for documentation of safety. Pain, discomfort, fatigue will be assessed at the start and end of each experimental session on a 11-point visual analogue scale ranging from 0 (none) to 10 (worst). Physical and cognitive demand assessment data will be recorded as well. The progress note will also document experimental session details (e.g., task performed, date, time etc.). The data collected through this survey will help monitor safety and comfort of using device on a session-by-session basis throughout the training period.

All collected assessment data forms will be de-identified and only include the coded-name for each participant.

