#### Statistics

Descriptive analyses will be used for Aim 1. For Aim 2, outcome measures will be analyzed using separate paired t-test (exoskeleton vs. no-exoskeleton walking). We also plan to plot the trend at pre-and post- training for all outcome measures for each subject (without exoskeleton). Significant level will be set at .05.

This is a pilot study therefore no data is available to calculate sample size. The reason to enroll 15 subjects is based on the limited funds awarded to this project. We anticipate that the data from this study will allow for performance of power analysis to determine effect size and sample size for future studies.

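### Aim 2: the order of walking with and without the exoskeleton at post-assessment is not stated or balanced in the protocol, and the paired t-tests have no order term

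*Combined protocol and SAP*

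**What the plan says.** Items 8, 9 and 10 of Outcome Measures (Timed Up and Go, 6-minute walk, Timed 25 Feet Walk) each state: "This task will be formed without using exoskeleton at pre-assessment and with and without exoskeleton at post-assessment". The schedule table in Study Design and Procedures has one post-treatment visit, Visit 18.

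Some test conditions are fixed:
- The assistive device is the same in both conditions of the reaction-time task: "Subjects will with and without EKSO (use same assistive device) at their preferred speed".
- In the 25-foot walk, comfortable pace comes before maximal pace, and "Resting periods will be provided between trials".
- In the 6-minute walk, "Subjects can slow down or stop to rest if they feel like", and "we will measure physical demands and cognitive demand in separate trials or sessions".

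None of these says whether the device or the unassisted walk comes first. The only text on recording session details, "The progress note will also document experimental session details (e.g., task performed, date, time etc", is in the section on participant status after each training session.

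The Statistics section says that for Aim 2 "outcome measures will be analyzed using separate paired t-test (exoskeleton vs. no-exoskeleton walking"). It then adds: "We also plan to plot the trend at pre-and post- training for all outcome measures for each subject (without exoskeleton"). No order or period term is mentioned.

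**The concern.** A within-person comparison of two conditions at one visit is a two-period crossover in miniature. The second walk may be slower because of fatigue or better because of practice. If the order varies between participants, that effect can be estimated and removed. If everyone has the same order, the t-test credits it to the device or holds it against the device, and no later analysis can separate the two.

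Fatigue is a fair worry on the protocol's own terms: the Objectives expect the device to prevent or delay it, and participants have EDSS scores of 6 to 7.5.

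The paired t-tests are the only inferential analysis planned. The Statistics section also intends the data to supply an effect size for future studies, so an order effect left in the estimate would carry into their sample sizes.

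**Working it through.** **Inputs from the documents.** n = 15 (Study Population); paired t-test at 0.05 (Statistics). Sidedness is not stated; I take two-sided. The plan gives no SD, effect size or power, and sets n = 15 by available funds, so there is no figure of its own to reproduce.

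**Assumptions.** Work in units of the SD of the paired difference (device minus no device) within an order. An order effect s adds +s to that difference in one order and −s in the other. I use s = 0.25, 0.5 and 0.75. These values are chosen to show sensitivity; nothing in the documents supports any of them. Power is shown at a true device effect of d = 0.8, also a chosen value.

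**1. All 15 in one order, no device effect.** The t statistic is noncentral with df = 14 and noncentrality s√15; the critical value is 2.145.

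| s | s√15 | False-positive rate |
|---|---|---|
| 0.25 | 0.968 | 14.7% |
| 0.5 | 1.936 | 43.8% |
| 0.75 | 2.905 | 77.1% |

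**2. Mixed order, plain paired t-test.** With k participants in the larger order, the share of s left in the estimate is (2k − 15)/15. False-positive rates are from 400,000 simulated trials per cell, except the single-order row.

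| Split | Share of s left | s = 0.25 | s = 0.5 | s = 0.75 |
|---|---|---|---|---|
| 15/0 | 100% | 15% | 44% | 77% |
| 12/3 | 60% | 8% | 15% | 25% |
| 10/5 | 33% | 5% | 6% | 7% |
| 8/7 | 7% | 4% | 3% | 2% |

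At 8/7 the plain test is conservative because the order effect goes into the variance. The expected sample variance is 1 + s² × 15 × (1 − 1/225)/14 = 1 + 1.067s², which is 1.07, 1.27 and 1.60 at the three values of s.

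**3. Power at d = 0.8, plain test.** With no order effect, noncentrality is 0.8√15 = 3.098, df = 14, and power is 82.1%. At 8/7 the mean also shifts by ±s/15, so the direction matters:
- larger group's order favours the device: 82% / 78% / 71%;
- larger group's order goes against the device: 79% / 71% / 58%.

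**4. Power at d = 0.8, with a period term.** The estimate is the mean of the two order-group means. Its SE, relative to the plain test with no order effect, is √[(15/4)(1/k + 1/(15 − k))], with df = 13.

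| Split | SE factor | Power |
|---|---|---|
| 8/7 | 1.002 | 81.5% |
| 10/5 | 1.061 | 77.0% |
| 12/3 | 1.250 | 63.1% |
| 15/0 | not estimable | – |

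These powers do not depend on s. Simulated type I error at 8/7 is about 5%. The effect detectable with 80% power moves from 0.778 SD (plain test, no order effect) to 0.784 SD (8/7 with the term).

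**The case against.** **The order may be set elsewhere.** Quality control and assurance promises written procedures for all tests, and Attachments lists case report forms; neither is shown. That stands, so the supportable claim is that the protocol does not state the order. It does not dispose of the point: a consistent procedure could mean one fixed order for everyone, which is the worst case above, and the Statistics section would still have no order term.

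**The mechanism may be weak.** A reader might count two conditions × two demand measures × 6 minutes = 24 minutes of walking in one sitting. The documents do not support that, because item 9 allows separate sessions. Changing condition also means donning or doffing the device. Exoskeleton Training allows 30 minutes for setup, donning and doffing, though for training sessions and not as a recovery period. The 25-foot walk has rests between trials, the 6-minute walk allows rest within it, and 15 device sessions beforehand limit practice effects. All this may shrink an order effect. None of it sets recovery between the two device conditions, and the Timed Up and Go has no rest text.

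**The comparator.** A reader might infer that the t-test could use the pre-assessment unassisted value and so mix the device with three weeks of training. The documents do not say so. Both conditions are measured at post-assessment, and the Statistics section gives the pre/post unassisted values a separate use, in plots. The same-visit pair is the natural reading; only an explicit sentence is missing.

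**Unassisted first for everyone would protect the pre/post comparison.** That is a defensible preference, since recovery of walking is the stated purpose. But those data are only plotted, whereas the device contrast is formally tested.

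**Conclusion.** The concern holds. The protocol neither states nor balances the order of the two post-assessment conditions, and the planned test cannot separate order from device if one order is used throughout.

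The 15% / 44% / 77% figures are conditional on three things: all 15 share one order, the order effect has the assumed size, and there is no device effect. They are not a forecast of bias. The documents do not show that one order will predominate, and the size and direction of any order effect are unknown. It would be wrong to infer that the Aim 2 result must be biased or that the pilot is unsound.

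What can be said firmly is that balancing the order and fitting a period term removes a common order effect at almost no loss of power (82.1% to 81.5% at d = 0.8). It should be done, as a cheap improvement to a pilot.

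**What to change.** 1. Randomise participants 8/7 to device first or device last at post-assessment. Keep each person's order for every walking test and, if demand measures are taken in separate sessions, in each session. State whether conditions are run in blocks or alternated within each test, since this sets the number of device changes.
2. Record the order. Use a standard rest between conditions, with its length set by the investigators.
3. In Statistics, analyse the paired difference with a period (order) term, and say that this removes a common order effect but not unequal carry-over.
4. In the same section, name the post-assessment unassisted value as the comparator.
5. Mark the order on the pre/post plots.

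**Cost.** A 15-line allocation list, one recorded field, one model term, one degree of freedom and an SE factor of 1.002. No extra participants are needed. The real trade-off is that seven or eight people do their unassisted post walks after device walks, so their pre/post plots are less comparable. The rest limits unequal carry-over but does not remove it.

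**Lighter option.** Recording the order and stating the rest without randomising is weaker: at a chance 12/3 split the adjusted power at d = 0.8 is 63%, and if all share one order no adjustment is possible.
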